## 10.6 Sample Size Estimates

Using ANOVA with repeated correlated measures improves power in clinical trials. The 1 year correlation with baseline repeated measures ranged from 0.3 to 0.5 in our pilot data. The effect size for candesartan relative to lisinopril was 0.48 [mean difference 12 (pooled SD 25 sec)] for TMT-B, 0.41 [mean 5.5(13)] for cerebral blood flow and 0.24 [mean 0.30(1.2)] for vasoreactivity to CO2 in our pilot study. Using a 2-sided  $\alpha = 0.05$ , we estimate that a sample size of 140 will give us 80% power to detect at least 0.24 effect size. To account for dropout rate of 10-15% and a 55% prevalence of eligible subjects, we estimate that we need to screen 332 and enroll 160 to achieve a 140 final sample size.

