### **6.3 Neuropsychological assessment:**

(i) Executive function will be assessed using the NINDS-initiated EXecutive Abilities: Measures and Instruments for Neurobehavioral Evaluation and Research or “EXAMINER” tool box. This test battery reliably and validly assesses executive function in clinical trials [<http://examiner.ucsf.edu/>]. The battery includes 11 tasks that generate 15 primary variables. Within this set, the EXAMINER investigators identified tasks measuring four domains that fit well in a single factor model of executive function: working memory, inhibition, set shifting, and fluency. The EXAMINER battery has excellent psychometric properties with test-retest reliability of over 0.9 and correlates by over 0.60 with an informant-based measure of day-to-day executive functioning, the Frontal Systems Behavior Scale. The parts of EXAMINER that we selected include:

- 1) Flanker task (inhibition) which involves responding to a central stimulus while ignoring flanking stimuli that are either compatible or incompatible with the central stimulus.
- 2) Set-shifting, a measure of mental flexibility assessing the subject's ability to attend to the specific attributes of compound stimuli, and to shift that attention when required.
- 3) Spatial 1-Back test assesses spatial working memory and
- 4) Dot Counting test assesses verbal working memory.
- 5) Verbal Fluency will be tested using a List Generation test which require the participant to generate words beginning with a specific letter, and category fluency in which the participant generates words from a specified category (e.g., animals, fruits).

Data will be scored using an open source web-based data management and scoring system available through the EXAMINER project Using item response theory, a single composite executive function score will be calculated from the available data points.

(ii) To assess additional cognitive domains/mood, we will use these tests included in the National Alzheimer's Coordinating Center Uniform Data Set.

- 1) Hopkins Verbal Learning Test will be used to assess memory domains.
- 2) Digit Span Test (DST) is a brief task that assesses attention.
- 3) Boston Naming Test assesses language by measuring ability of naming a visual confrontation drawing (15 items).

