- 4) Trail Making Test: will be used as an additional measure of executive function.
- 5) Center for Epidemiologic Studies Depression Scale (CESD), and consists of 20 items, each scored from 0 to 3 points and higher scores indicate greater depressive symptoms.

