#### 10.4 Outcomes

Table 3 provides a list of main outcomes. Other Analyses' variables: Logical memory, digit span, DSST, WMH volume, regional brain measures

**Table 3:** Independent, primary and secondary outcomes and other variables to be used in the analyses

Independent:	Randomization Group (Candesartan vs Lisinopril)
Primary outcome:	Executive function (EXAMINER score)
Secondary Imaging outcomes:	Perfusion, CO2 VR, VMR, FA, MD, DTT t-scores, rs-fMRI
Mediators:	CIMT, stiffness, inflammatory markers, EPC
Tertiary outcomes:	memory, digit span, DSST, WMH volume, regional brain measures
Stratification variable:	Race, number of antihypertensive medications
Covariates:	Prior stroke and prior use of ACEI/ARB
Safety:	AE, SAE, incident dementia

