#### Outcome Analysis

(a) Candesartan and cognitive/neuroimaging outcomes: General linear models will be used to compare the candesartan and lisinopril groups. Our main explanatory variable is the indicator for treatment group. Dependent variables will be the 12-month cognitive and neuroimaging measurements. For the cognitive analyses, our primary outcome is the executive function score derived using item response theory as outlined above in the EXAMINER methodology to account for education, age, and race influences on measures of executive abilities (developed by our collaborator, [name] team). For the cognitive outcome Mixed models with repeated measures (3 measurements) will be used. This procedure allows us to model the covariance structure to account for the potential variability across subjects in times of follow-up visits. Our main explanatory variable is the indicator for treatment group. The test of treatment effects on trial outcomes will be an interaction of treatment by visit (baseline,12 months follow-up). The main covariate adjustments will include history of prior stroke and prior exposure to ACEI/ARB. Additional covariate adjustments will be selected based on baseline statistically significant differences between the 2 randomized groups. The neuroimaging outcomes include measures of global perfusion, reactivity, FA, MD, and tractography metrics described above. **Table 3** provides a list of main variables. The multivariate models of the neuroimaging analysis will include the baseline values of the 12-month outcome variable, randomization stratification variables and other covariates that are significantly differ (at p<0.05) between the 2 groups at baseline. We will assess if the effects of randomized treatment are independent of blood pressure by comparing models with and without blood pressure change from baseline to 12 months. Summary statistics will include the model-adjusted mean and 95% confidence interval for each treatment group, and the mean (95% confidence interval) group difference on each 12-month outcome, as well as a p-value for group differences. All tests of significance on treatment group comparisons will use a two-sided alpha of 0.05.

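### Section 10.6 does not show the power of the primary EXAMINER comparison, and its 80% power at an effect size of 0.24 does not follow from its own scale and correlation

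*Combined protocol and SAP*

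**What the plan says.** Section 10.6 reports pilot effects for three measures. One is cognitive: "The effect size for candesartan relative to lisinopril was 0.48 [mean difference 12 (pooled SD 25 sec)] for TMT-B". The other two are MRI measures: cerebral blood flow, 0.41 (5.5 with SD 13), and vasoreactivity to CO2, 0.24 (0.30 with SD 1.2). The section adds that "The 1 year correlation with baseline repeated measures ranged from 0.3 to 0.5 in our pilot data", without naming the measure, and concludes that "we estimate that a sample size of 140 will give us 80% power to detect at least 0.24 effect size".

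Table 3 in section 10.4 makes the EXAMINER score the primary outcome. The Trail Making Test is in none of its outcome rows; the tertiary row reads "memory, digit span, DSST, WMH volume, regional brain measures". Section 6.3 lists the Trail Making Test outside the selected EXAMINER tasks and says it "will be used as an additional measure of executive function".

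Under Outcome Analysis in section 10.5, the cognitive outcome goes into a mixed model with three measurements. The treatment effect is tested as treatment by visit, baseline against 12 months. On the significance level: "All tests of significance on treatment group comparisons will use a two-sided alpha of 0.05". The only repeatability figure for the primary outcome is in section 6.3: "The EXAMINER battery has excellent psychometric properties with test-retest reliability of over 0.9".

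**The concern.** A power statement should describe the primary comparison. That requires an effect and an SD for EXAMINER and, because the test is of change from baseline, EXAMINER's own correlation between baseline and 12 months. Section 10.6 attributes none of these to EXAMINER.

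The number it prints is also doubtful. An effect of 0.24 SD is small for 70 per arm, and correlations of 0.3 to 0.5 bring little gain in precision. If the 80% is wrong as written, a null EXAMINER result could be taken as good evidence against an effect of about a quarter of an SD when the trial had little chance of detecting one. The interim analyses for efficacy and futility in section 10.3 are also on EXAMINER, and a futility judgement needs a credible detectable difference.

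**Working it through.** **Inputs.** 70 per arm (Sample Size and Population); two-sided alpha 0.05 (10.5, 10.6); effect 0.24 and r = 0.3 to 0.5 (10.6); baseline-to-12-month contrast (10.5).

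**Scale.** The pilot effects are mean difference over SD: 12/25 = 0.48; 5.5/13 = 0.42 (printed 0.41); 0.30/1.2 = 0.25 (printed 0.24). So 0.24 is first read on that scale.

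**Reproducing the 80%.** A plain 12-month comparison with 70 per arm has noncentrality 0.24/√(2/70) = 0.24/0.169 = 1.42. Power is 29.2% (noncentral t, 138 df). Three variants in the normal approximation also fall short:

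- one-sided alpha: 41%
- 140 per arm: 52%
- mean of the two follow-up visits, adjusted for baseline: 48% (r = 0.3) to 52% (r = 0.5)

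**Using the correlation.** With the effect in 12-month SD units, multiply the SD by k = √(2(1−r)) for the change contrast, or k = √(1−r²) for baseline adjustment. Noncentrality is 1.42/k. For the change contrast, r = 0.3 gives k = 1.183 and noncentrality 1.20; r = 0.5 gives k = 1 and 1.42. For baseline adjustment, the values are k = 0.954 and 1.49, and k = 0.866 and 1.64. Reaching 80% needs about 2.82.

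| r | Power at 0.24, change contrast | Power at 0.24, baseline-adjusted | Detectable at 80%, change contrast |
|---|---|---|---|
| 0.3 (stated) | 22% | 32% | 0.56 SD |
| 0.5 (stated) | 29% | 37% | 0.48 SD |
| 0.7 (assumed) | 45% | 51% | 0.37 SD |
| 0.9 (assumed) | 88% | 90% | 0.21 SD |

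With baseline adjustment, the detectable difference at r = 0.3 to 0.5 is about 0.45 to 0.41 SD.

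**What 80% at 0.24 would need.** k = 1.42/2.82 = 0.504. So r = 1 − 0.504²/2 = 0.87 for the change contrast, or r = √(1 − 0.504²) = 0.86 with baseline adjustment. Alternatively, at r = 0.3 to 0.5 (normal approximation), it needs 382 to 273 per arm for the change contrast, or 249 to 205 with baseline adjustment.

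**Readings that return 80%.** If 0.24 is Cohen's f in a two-group ANOVA, the noncentrality parameter is 140 × 0.24² = 8.064 and power is 80.5%. For two equal groups, f = 0.24 is a mean/SD effect of 0.48, and 35 × 0.48² = 8.064 confirms it. This reading does not use the correlation. One other run gave the same result: half of 0.24 entered as f for a two-visit interaction at r = 0.5, where 140 × 0.12² × 2/(1 − 0.5) = 8.064. That also corresponds to a 0.48 SD difference in change between arms, and at r = 0.3 it gives only 66%. Entering f = 0.24 in the repeated-measures formulas with two or three visits gives 90% or more.

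**The case against.** The best defence is that 0.24 is Cohen's f. The arithmetic then works and N = 140 is reasonable for a 0.48 SD difference. But the plan does not say so. The same paragraph uses 0.24 on the mean/SD scale for vasoreactivity, so a reader will take the two figures as the same quantity.

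A second defence is that EXAMINER may be very stable. At r = 0.9, power at 0.24 would be 88%. That is fair, and it means the calculation does not show EXAMINER to be underpowered. But the figure of over 0.9 in section 6.3 is test-retest reliability with no interval stated, not a one-year correlation in this population. It cannot replace the 0.3 to 0.5 that section 10.6 relies on. Nor does it support a headline about how far power swings between the two.

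Third, TMT-B measures the same construct, and planning from a proxy is legitimate. That stands. It does not supply EXAMINER's SD or correlation.

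A reader might infer more than the documents support:

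- *That the trial was sized on TMT-B.* As printed, 0.24 is the vasoreactivity effect, and vasoreactivity is a secondary outcome in Table 3. The match with TMT-B's 0.48 arises only on the undeclared readings above.
- *That TMT-B has no planned analysis.* Section 6.3 plans the test, Table 2 schedules neuropsychological measures at baseline, 6 and 12 months, and section 10.5 models the 12-month cognitive measurements. Table 3 is described as a list of main outcomes. What is missing is a rank for TMT-B.
- *That the correlation comes from TMT-B and the MRI measures.* Section 10.6 attributes it only to pilot data.

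**Conclusion.** The point holds in two parts. First, section 10.6 attributes no effect, SD or one-year correlation to EXAMINER, so power for the primary outcome is unknown rather than shown to be low. Second, 80% power at 0.24 is wrong as written: on the section's mean/SD scale and at its stated correlation, power is 22-29% for the planned contrast and 32-37% with baseline adjustment.

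This rests on 70 analysed per arm, two-sided 0.05, equal SDs at baseline and 12 months, and an effect expressed in 12-month SDs. If the pooled SD were instead an SD of change, power at 0.24 would be 29% whatever the correlation. The two-visit formulas simplify the three-measurement model, but they match the contrast that section 10.5 names. The values at r = 0.7 and 0.9 are illustrations.

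**What to change.** In section 10.6, replace the statement of 80% power at 0.24 with the detectable difference for the treatment-by-visit contrast at N = 140, 80% power and two-sided 0.05: 0.56 to 0.48 SD at the stated r of 0.3 to 0.5. Add 0.37 SD at r = 0.7 and 0.21 SD at r = 0.9, both labelled as assumptions. Say that no EXAMINER-specific pilot inputs were available, and name the measure behind the correlation. If Cohen's f was meant, say so and give the mean/SD equivalent of 0.48.

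This is a wording change. N, visits and alpha stay as they are. The cost is that one favourable figure becomes a less favourable range.

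Optionally, list TMT-B in Table 3 as a named non-primary cognitive outcome. It is already collected, and the cost is one more non-primary comparison to report.

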## 4.2 Exclusion Criteria

- (1) Intolerance to candesartan or lisinopril ;
- (2) SBP >200 or DBP >110 mm Hg;
- (3) Renal disease or hyperkalemia (SCr >1.99 mg/dl or K > 5.5 meq/dl);
- (4) Active medical or psychiatric problems (An active problem is one that requires medical attention and is deemed as a safety risk by the study physician, for example current cancer treatment, infections such as pneumonia, current gastrointestinal or other internal bleeding, HIV treatment, hematological disease, Parkinson's disease, multiple sclerosis)
- (5) Uncontrolled congestive heart failure [shortness of breath at rest or evidence of pulmonary edema on exam];
- (6) History of stroke in the past 3 years (self-reported clinical stroke within the past 3 years/ incidental infarcts on MRI scanning is allowed);
- (7) Inability to perform the study procedures (those with contraindications for MRI will be enrolled but will not undergo the MRI; those with history of asthma, COPD, or significant pulmonary disease will not undergo the CO2-reactivity protocol);
- (8) Women of childbearing potential
- (9) Current use of acetylcholine-esterase inhibitors or NMDA receptor antagonist (memantine) or a diagnosis of dementia self-report or care-giver report
- (10) In those who lack decision capacity, a *study surrogate* who can sign on their behalf will be required. Since we are enrolling only those with MCI, we anticipate that most participants will have decision capacity
- (11) Current use of Lithium, as most antihypertensive classes may lead to increased lithium toxic levels.

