### **10.3 Interim analyses**

In addition to the planned regular reporting to the DSMB of trial conduct and safety (see Data and Safety Monitoring Plan), formal interim analyses will be conducted for efficacy and futility on the primary trial outcome (EXAMINER score). To avoid un-blinding investigators, the analysis will be conducted by an independent data analyst/statistician; this un-blinded statistician will present the interim outcome analysis to the DSMB in a closed-session (not involving trial investigators). We will conduct the interim outcome analyses when 25% and 50% of the sample has completed their 12-month assessments. We will use an alpha spending

function approach with O'Brien-Fleming sequential boundaries to preserve the overall two-sided alpha error rate of 0.05. O'Brien-Fleming alpha levels will be 0.0051 and 0.0415 (2 analyses). If the boundary is crossed at the first interim analysis, the DSMB will convene to decide on termination or continuation of the trial based on efficacy.

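### The claim of 80% power at effect size 0.24 with 140 participants does not reproduce: on the plan's own inputs power is 22–37%, and 80% power needs an effect of 0.41–0.56.

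*Combined protocol and SAP*

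**What the plan says.** Section 10.6 reports three pilot effects for candesartan against lisinopril, each with a mean and an SD: 0.48 for TMT-B (12 over 25), 0.41 for cerebral blood flow (5.5 over 13) and 0.24 for CO2 vasoreactivity (0.30 over 1.2). On correlation it says: "The 1 year correlation with baseline repeated measures ranged from 0.3 to 0.5 in our pilot data". At two-sided alpha 0.05 it concludes: "we estimate that a sample size of 140 will give us 80% power to detect at least 0.24 effect size". The 140 is the number left after dropout from 160 enrolled, 70 in each group (Sample Size and Population; section 3).

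Section 10.5 (Outcome Analysis) names two kinds of test. For cognition, in a mixed model with three measurements: "The test of treatment effects on trial outcomes will be an interaction of treatment by visit (baseline,12 months follow-up"). For imaging, which includes vasoreactivity: "The multivariate models of the neuroimaging analysis will include the baseline values of the 12-month outcome variable". It adds: "All tests of significance on treatment group comparisons will use a two-sided alpha of 0.05".

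**The concern.** A two-group comparison with 70 per arm normally reaches 80% power at a standardized difference a little under one half. A claim of 80% power at half that size needs a very large gain in precision from the repeated measures. Correlations of 0.3 to 0.5 cannot supply it.

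This is the only power statement behind the sample size, and its wording implies that all three pilot effects are covered. Vasoreactivity is named in Hypothesis 2 and listed as a secondary outcome in Table 3. A reader who relies on section 10.6 would take a null vasoreactivity result as fairly strong evidence against the pilot effect, when the trial had little chance of detecting it.

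**Working it through.** **Inputs.** n = 70 per arm, two-sided alpha 0.05, effect d = 0.24 in SD units, correlation ρ = 0.3 to 0.5 (section 10.6), tests from section 10.5. The pilot SDs are taken as SDs of the measurement at one time; section 10.6 does not say which kind they are.

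**Formula.** Noncentrality λ = (d/s) × √(n/2), with √(70/2) = 5.916. The residual SD s, in units of the outcome SD, depends on the test:

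- 12-month value alone: s = 1
- baseline-adjusted 12-month value: s = √(1 − ρ²), which is 0.954 at ρ = 0.3 and 0.866 at ρ = 0.5
- treatment-by-visit contrast, baseline to 12 months: s = √(2(1 − ρ)), which is 1.183 at ρ = 0.3 and 1.000 at ρ = 0.5

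For the unadjusted test λ = 0.24 × 5.916 = 1.420. The normal approximation gives power Φ(1.420 − 1.960), about 29%. Noncentral t results (138 degrees of freedom, 137 with baseline adjustment):

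| Test | ρ | λ at 0.24 | Power at 0.24 | Effect for 80% power | Total N for 80% at 0.24 | Power at 0.48 |
|---|---|---|---|---|---|---|
| Unadjusted | – | 1.420 | 29% | 0.48 | 548 | 81% |
| Baseline-adjusted | 0.3 | 1.488 | 32% | 0.45 | 498 | 84% |
| Baseline-adjusted | 0.5 | 1.640 | 37% | 0.41 | 412 | 90% |
| Treatment-by-visit | 0.3 | 1.200 | 22% | 0.56 | 766 | 66% |
| Treatment-by-visit | 0.5 | 1.420 | 29% | 0.48 | 548 | 81% |

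A simulation of the 12-month change contrast with three equally correlated visits (20,000 runs) gave 22.2% and 28.9% at 0.24, in agreement with the last two rows. For the pilot blood-flow effect of 0.41, baseline-adjusted power is 71–79%.

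**Trying to reproduce the 80%.** On the mean/SD scale, with the stated correlations, no two-group variant reaches it:

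- all 160 enrolled complete: 25–41% across the three tests
- d = 0.25, the exact value of 0.30/1.2: 24–40%
- one-sided test: at most 50%
- group main effect over three visits: 41–49%
- mean of the 6- and 12-month values, adjusted for baseline: 47–51%

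The figure does appear under other readings:

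- Cohen's f = 0.24 with N = 140 gives 80.5%; for two equal groups d = 2f, so this is d = 0.48.
- A one-sample or paired test on 140 people at 0.24 gives 80.5%, but that is not a comparison of two arms.
- A repeated-measures interaction test with f = 0.12 entered directly (two measurements, ρ = 0.5) gives 80.5%, and that f corresponds to a 0.48 SD difference in change.

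**Correlation needed.** For 80% power at 0.24, ρ must be about 0.86 (baseline-adjusted) or 0.87 (treatment-by-visit).

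**Further sensitivities.**

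- Section 10.3 says "O'Brien-Fleming alpha levels will be 0.0051 and 0.0415 (2 analyses"). If 0.0415 is the final-look level for the primary outcome, the treatment-by-visit detectable effect is 0.49–0.58, and unadjusted power at 0.48 falls to 78%.
- Not everyone contributes imaging: "those with contraindications for MRI will be enrolled but will not undergo the MRI", and people with lung disease skip the CO2 protocol (section 4.2). The plan gives no rate. If 10–30% are missing (an assumption), baseline-adjusted power at 0.24 is 23–34%; at 20% it is 26–31%.

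**The case against.** Four points can be made for the plan.

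**EXAMINER may correlate far more strongly over time.** Section 6.3 says: "The EXAMINER battery has excellent psychometric properties with test-retest reliability of over 0.9". If the 1-year correlation were 0.9, power at 0.24 would be 88–90%; at 0.8 it would be 61–65%. This stands as a limit for the primary outcome. However, section 6.3 does not call the figure a 1-year correlation, section 10.6 does not use it, and it cannot help vasoreactivity, the outcome that supplies the 0.24.

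**The type of SD is not stated.** If the pilot SDs are SDs of change, treatment-by-visit power is 29% at any correlation, and baseline-adjusted power is 37–42% (detectable effect 0.38–0.41). The range would then be 29–42% instead of 22–37%. The assumption should be disclosed, but the conclusion does not change.

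**Section 10.6 invokes repeated-measures ANOVA.** A test averaged over visits does better, at 41–51% in the variants above. That is still well short of 80%, section 10.5 specifies the baseline-to-12-month contrast, and MRI is done only at baseline and 12 months (Table 2).

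**The consequence is bounded.** Vasoreactivity is secondary, and power at the TMT-B effect of 0.48 is 81% unadjusted. The 95% confidence intervals required by section 10.5 would show the imprecision: the baseline-adjusted half-width is about 0.29–0.32 SD. All of this is true. It limits the damage but does not make the power statement correct.

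**Conclusion.** The concern holds. With 70 per arm, two-sided alpha 0.05, effects on the mean/SD scale and a correlation of 0.3 to 0.5, the design does not have 80% power at 0.24 for any test in section 10.5. The low end of the 22–37% range is the treatment-by-visit test at 0.3; the high end is the baseline-adjusted test at 0.5. Under the stated imaging model the vasoreactivity effect would be missed 63–68% of the time.

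The exact range assumes that the pilot SDs are cross-sectional. For the EXAMINER score the shortfall also assumes that the pilot correlations carry over, which the documents neither state nor rule out. The origin of the error is not established. A confusion between Cohen's f and the mean/SD scale would explain it, but section 10.6 gives no sign of an f scale and ties 0.24 to 0.30 over 1.2.

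**What to change.** Delete the claim of 80% power at 0.24. State which test, effect-size scale, type of SD and correlation the calculation uses, then give the detectable effect for each test in section 10.5. If the pilot SDs are confirmed as cross-sectional, the text could read:

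> With 140 completers (70 per arm), two-sided alpha 0.05 and a baseline-to-12-month correlation of 0.5 to 0.3, there is 80% power to detect a standardized difference (mean difference/SD) of 0.41–0.45 for baseline-adjusted imaging outcomes and 0.48–0.56 for the treatment-by-visit test.

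In addition:

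- If the final-look alpha for the EXAMINER test is below 0.05, use it (0.49–0.58 at 0.0415).
- State that power for the 0.24 vasoreactivity effect is 32–37% on all 140, and lower on the number expected to complete the MRI and CO2 protocol.
- If a higher 1-year EXAMINER correlation is assumed, give its value and source and recompute.

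The cost is a rewording of section 10.6 and a less favourable stated figure. No participants are added, and conduct and analysis do not change.
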